11.6 Recording of Adverse Events

All AEs will be assessed for seriousness, expectedness and relatedness by the PI or designee, recorded in the CRF and notified to the CI/trial manager once the PI becomes aware of the AE. All AEs will also be recorded in the participant's medical notes.

11.7 Adverse Event Reporting

An SAE occurring to a research participant will be reported to the main REC where in the opinion of the CI the event was:

- a) Related- that is, it resulted from administration of any of the research procedures, and
- b) Unexpected- that is, the type of event is not listed in the protocol as an expected occurrence.

Reports of related and unexpected SAEs will be submitted to REC within 15 days of the CI becoming aware of the event, using the SAE report form for non-CTIMPs published on the HRA website available at: http://www.hra.nhs.uk/resources/during-and-after-your-study/progress-and-safety-reporting/. The CI will include a report on the safety of participants in the annual progress report.

11.8 Follow-up of Adverse Events

The AE reporting period for the trial begins upon enrolment of a participant into the trial and ends at month 12. All AEs assessed by the PI or designee as being related and unexpected will be followed until they are resolved or are clearly determined to be due to a participant's stable or chronic condition or intercurrent illness(es). The CRF should be updated with the date and time of resolution or confirmation that the event is due to the participant's illness as soon as this information becomes available.

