8.5 Participant Timeline

Eligibility will be determined at the screening visits. Surgery in Group 1 will take place at Day 0 with surgical review on days one and seven and study visits for both Groups at months one, three, six and 12. As the presence of the device is obvious to the casual observer, it will not be possible to mask assessors. Participants can also not be masked to the intervention. However, the final BCDVA measurement at 12 months will be duplicated by an additional observer independent to the trial and this measurement will be used for the primary analysis. BCDVA (primary outcome) will be measured with 4-meter ETDRS charts. Assessment at screening will include medical history, ophthalmic examination, confrontation visual field testing, visual acuity, reading speed, refraction, contrast sensitivity, assessment with x2.5 external telescope for distance and near vision, assessment for ocular dominance, binocular visual function, endothelial cell density, ocular coherence tomography (OCT) with volume scan, colour fundus photography, IVI, and EQ-5D-5L. Fundus fluorescein angiography (FFA) will be carried out in addition to OCT at baseline and only subsequently if clinically indicated as OCT cannot be performed post implantation of the device. The order of screening examinations will follow as per Figures 3 and 4, however, this may vary at site depending on the location of equipment. The detailed schedule is shown below in Table 2.

If all inclusion criteria are met at both screening visits, participants will be enrolled into the study. The required clinical information will be returned to the lead site (NICTU) and the study eye will be selected. The participant will be informed within 72 hours regarding which eye has been selected as the study eye and will be provided with a date to attend for Nd:YAG capsulotomy in the study eye, if not already done. After the participant has undergone the laser treatment, the Principal Investigator (PI) or designee will contact the CTU to determine group allocation. The participant will then be notified within 72 hours post laser treatment regarding group allocation.

Group 1 Care Pathway:

- Day 0: Surgery (surgical implantation of OriLens device)
- Day 1: Surgical review
- Day 7: Surgical review
- Assessments will be carried out at Months 1, 3, 6 and 12
- Low vision training at months 1, 3 and 12

Group 2 Care Pathway

- Day 0: No procedure

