- Assessments will be carried out at Months 1, 3, 6 and 12 (beginning approximately six weeks post randomisation)
- Low vision training at months 1, 3 and 12

Figure 2. Study Schematic Diagram

[figure not shown]

Table 2. Schedule of enrolment, interventions and assessments

TIMEPOINT	Screening									v	, v	*
	Pre- screen	Screening 1 Day -45 to -20	Screening 2 Day -45 to -20	Day -20 to -7	Dау -7 to -1	Day 0	Day 1	Day 7	Month 1*	Month 3*	Month 6*	Month 12*
Pre-screening Questionnaire	Х											
Informed consent		х										
Medical History [†]		х			XX		XX	ХХ	Х	Х	Х	Х
Ophthalmic Examination‡		х			XX		XX	ХХ	Х	Х	Х	Х
Visual field by confrontation		х										
Visual Acuity (Distance)		х			XX		XX	XX	Х	х	х	Х
Visual Acuity (near), reading speed		х						XX	Х	х	х	Х
Refraction, contrast sensitivity		х						ХХ	Х	Х	Х	Х
Testing with external telescope		х										
Fundus photography		х										Х
ОСТ		х										
FFA		х										
Specular microscopy			х									Х
Microperimetry			х									
Assessment of PRL			х									
Orthoptic assessment #			х									
EQ-5D-5L			х								х	Х
IVI			х								х	Х
Health service use questionnaire											х	Х
Eye Selection confirmation				х								
Nd:YAG Capsulotomy (if required)				Х								
Randomisation				Х								
Informed consent for surgery					ХХ							
Surgical procedure ∞						ХХ						
Spectacle prescription & voucher for glasses									Х		Х	**
Visual Rehabilitation Training									Х	Х		х
Adverse Events Check							XX	XX	Х	х	х	Х

X: Both groups; XX: Intervention group; **: Spectacles dispensed at participants own cost; *: Control group Month 1- Approximately 6 to 8 weeks post randomisation, month 3- 14 weeks post randomisation, month 6- 6 to 7 months post randomisation, month 12- 12 to 13 months post randomisation; †: Medical history will include general medical history, ophthalmic medical history, blood pressure measurement and concomitant medication; ‡: Ophthalmic examination will include slit lamp assessment, pupillary assessment, intraocular pressure measurement and fundoscopy; #: Orthoptic assessment will include history of binocular vision anomalies, cover test, record of ocular movements, prism cover test, Bagolini glasses assessment, near point of convergence (NPC) assessment, measurement of horizontal fusional reserves and assessment of ocular dominance; ∞ : standard surgical report will be completed immediately post-op.

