8.7.2 Screening procedure

Potential participants will undergo a pre-screen to determine general suitability for the study. This will entail completion of a pre-screening questionnaire by an optometrist, ophthalmologist or General Practitioner (GP) of the potential participant's choosing. The completed pre-screening questionnaire will be sent by the potential participant to their nearest site and will subsequently be screened by the PI or delegated clinician as per the inclusion/exclusion criteria defined in the protocol. Potential participants will be sent a standard letter informing them that they may or may not be eligible for the study, dependant on further tests, and that the site will be in contact with them to arrange a suitable time to attend a screening appointment. Those who do not meet the initial inclusion criteria will be sent a standard letter to inform them of this.

Due to the number of screening examinations, two screening visits are required so as not to over burden the participant. The participant will not be expected to continue with screening if they do not meet the eligibility criteria as a result of any screening examination. It is anticipated that screening Visit 1 will last up to three hours and screening Visit 2, up to two hours. Those participants who meet the inclusion criteria and are enrolled into the study will receive reimbursement for their travel expenses at the end of the second screening visit. This will be a set amount for all participants.

Upon attending the first face-to-face screening appointment, the PI or designee will ask the potential participant whether they have any questions and whether they are still willing to participate in the study. If the patient agrees to participate, the PI or designee will obtain written informed consent prior to conducting screening tests. The following examinations will be conducted during the screening visits in the order as shown in Figures 2 and 3 as per the trial manual. However, the order may vary depending on the location of instruments at site.

[figure not shown]
- 1. Medical History⁺ and ophthalmic examination[‡]
- 2. Visual field by confrontation
- 3. Visual Acuity (distance and near), reading speed, refraction, contrast sensitivity
- 4. Testing with external telescope
- 5. Fundus photography
- 6. Ocular Coherence Tomography (OCT)
- 7. Fundus Fluorescein Angiography (FFA)
- 8. Specular microscopy

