10.2.2 Study Visits and Procedures

Pre-randomisation (Day -20 to -7) (Both groups)

Nd: YAG Capsulotomy in study eye (if not already done)

Pre-operative (Day -7 to -1) (Intervention group only)

Pre-op medical history assessment Visual acuity (distance only) and ophthalmic examination Informed consent for surgical procedure

Day 0 (Intervention group only)

Surgical procedure Standard surgical report (post-operatively)

Day 1 Post-operative (Intervention group only)

Medical history, ophthalmic examination Visual acuity (Distance only) Adverse events check

Day 7 Post-operative (Intervention group only)

Medical history, ophthalmic examination

Visual acuity (distance and near), reading speed, refraction, and contrast sensitivity Adverse events check

1 Month (approximately 6-8 weeks post randomisation) (Both groups)

Medical history, ophthalmic examination Visual Acuity (distance and near), reading speed, refraction, and contrast sensitivity Spectacle prescription dispensing and voucher for glasses Visual Rehabilitation training Adverse events check

3 months (approximately 14 weeks post randomisation) (Both groups)

Medical history, ophthalmic examination Visual Acuity (distance and near), reading speed, refraction, and contrast sensitivity Visual Rehabilitation training Adverse events check

6 months (approximately 6-7 months post randomisation) (Both groups)

Medical history, ophthalmic examination Visual Acuity (distance and near), reading speed, refraction, and contrast sensitivity Health related quality of life (EQ-5D-5L) Vision-related quality of life (IVI) Health service use questionnaire Spectacle prescription dispensing and voucher for glasses Adverse events check

12 months (approximately 12-13 months post randomisation) (Both groups)

Medical history, ophthalmic examination Visual Acuity (distance and near), reading speed, refraction, and contrast sensitivity Fundus photography Specular microscopy Health related quality of life (EQ-5D-5L) Vision-related quality of life (IVI) Health service use questionnaire Spectacle prescription dispensing Visual Rehabilitation training Adverse events check

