11.5 Eliciting Adverse Event Information

- Retinal vascular occlusion
- Anterior chamber cells
- Anterior synechiae
- Corneal transplant
- Cyclitic membrane
- Distorted pupil
- Epithelial heaping
- Flat anterior chamber
- Hypopyon
- Increased IOP requiring treatment
- Iris atrophy
- Iritis
- Pigment deposits on OriLens device
- Pupillary block
- Requirement for iridectomy/iridotomy
- Retinal detachment
- Secondary glaucoma

The PI or designee will record all directly observed AEs and all AEs spontaneously reported by the participant that are not related to underlying medical conditions. In addition, the participant will be asked about AEs at day one, day seven, and months one, three, six and 12 following implantation of the device.

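### The AE reporting period opens after the trial's own screening angiography, and no AE question is scheduled after the laser until Day 1 after surgery or, in controls, Month 1

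*Protocol*

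**What the plan says.** **Reporting period.** Protocol 11.8: "The AE reporting period for the trial begins upon enrolment of a participant into the trial and ends at month 12". Section 8.5 places enrolment: "If all inclusion criteria are met at both screening visits, participants will be enrolled into the study".

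**Screening angiography.** Section 8.7.2 says that "the PI or designee will obtain written informed consent prior to conducting screening tests". Section 8.5 says: "Fundus fluorescein angiography (FFA) will be carried out in addition to OCT at baseline and only subsequently if clinically indicated". Table 2 puts angiography in the column headed "Screening 1 Day -45 to -20".

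**Laser.** After enrolment and eye selection, the participant "will be provided with a date to attend for Nd:YAG capsulotomy in the study eye, if not already done". Section 10.2.2 lists one item for both groups before randomisation, at Day -20 to -7: "Nd: YAG Capsulotomy in study eye (if not already done"). No AE check stands beside it.

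**AE questions.** Section 11.5 requires directly observed and spontaneously reported AEs to be recorded, unless they relate to underlying medical conditions. It adds that "the participant will be asked about AEs at day one, day seven, and months one, three, six and 12 following implantation of the device". In Table 2 the AE check row starts at Day 1 for the implant arm and at Month 1 for both groups. The pre-operative visit (Day -7 to -1, implant arm only) has a history, distance acuity and an ophthalmic examination, but no AE check.

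**Assessment and analysis.** Every AE is assessed for relatedness (11.6). For reporting serious events to the ethics committee, related means caused by any research procedure (11.7). AEs are summarised by treatment. The list of anticipated events is headed as due to OriLens implantation; there is none for the laser or for angiography.

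**The concern.** The trial imposes two procedures before randomisation: angiography on those screened, and laser capsulotomy on everyone who has not already had it. The safety plan is built around the implant instead.

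For angiography, the participant has given trial consent and undergone a trial test, yet the stated period has not begun. This sits badly with 11.7, which treats harm from any research procedure as related.

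For the laser, the problem is when and how evenly events are found. The implant arm is first asked after a second procedure on the same eye. Controls are first asked weeks later, when a transient event may have passed. Increased intraocular pressure requiring treatment, intraocular inflammation, dislocation of the existing lens and retinal detachment all appear on the anticipated list for the OriLens. A laser event of one of these types that is first elicited after surgery could be taken for a device event. What is at stake is a complete safety record for trial procedures and a fair AE comparison by treatment.

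**Working it through.** There is no power or sample-size figure to reproduce. The check is the order of events plus day arithmetic on the visit windows.

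**1. Angiography against the reporting period**

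- Consent: Screening 1, before the tests (8.7.2, Table 2).
- Angiography: Screening 1, Day -45 to -20 (Table 2).
- Specular microscopy, which can still exclude a person (8.7.2): Screening 2, same window (Table 2).
- Enrolment: after both visits are passed (8.5).
- AE period opens: enrolment (11.8).

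Angiography therefore precedes the period. The uncovered interval between the two visits can be anything up to -20 - (-45) = 25 days. A person who has angiography and then fails on endothelial cell density never enters the period.

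**2. Laser against the reporting period**

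The order in 8.5 is enrolment, eye selection, laser, randomisation. The laser is inside the period, so 11.5 and 11.6 apply to any event that is observed or volunteered.

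**3. Time from laser to the first scheduled AE question**

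Implant arm, by Table 2 (laser Day -20 to -7, check Day 1):

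- shortest: 1 - (-7) = 8 days
- longest: 1 - (-20) = 21 days

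Implant arm, if surgery is at the limit of eight weeks after randomisation (7.1, 8.3.1):

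- 8 × 7 + 1 = 57 days after randomisation
- allocation is notified within 72 hours after the laser, so randomisation can follow the laser by up to 3 days: 57 + 3 = 60 days

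Controls (Month 1 at about 6 to 8 weeks after randomisation):

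- 6 × 7 = 42 to 8 × 7 = 56 days after randomisation
- with the same allowance, up to 56 + 3 = 59 days after the laser

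**4. Ascertainment by arm, up to and including Month 1**

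| | Implant arm | Control arm |
|---|---|---|
| Scheduled AE checks | 3 (Day 1, Day 7, Month 1) | 1 (Month 1) |
| Eye examination between laser and Day 0 | 1 (pre-operative) | 0 |

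For the same laser procedure, ascertainment is more frequent in the implant arm. It is also earlier when surgery follows the Table 2 windows. At the eight-week limit, the times to the first question are close (57 to 60 days against up to 59).

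**The case against.** The strongest reply is that most of the safety net exists. The laser falls within the period, and observed and volunteered events must be recorded whatever the procedure. The pre-operative examination comprises slit lamp, pupils, intraocular pressure and fundoscopy, so it could show a laser complication before the implant goes in. Every AE is assessed for relatedness. The laser precedes randomisation and is given to both groups where needed, so its true risk should balance on average. The protocol itself describes capsulotomy risk as negligible (7.1). All of this stands.

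It rules out three stronger readings that a reader might infer. First, that laser events escape AE collection: they do not; what is missing is a scheduled question. Second, that the trial keeps no safety record of procedures it imposes: 11.5 and 11.6 provide one for the laser. Third, that the AE comparison is biased against the device: no text attributes laser events to the implant, and no size or direction of bias can be derived. Angiography precedes randomisation, and its reactions before enrolment do not bear on the comparison of arms.

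It may also be said that enrolment is not formally defined, and 9.3 uses the word loosely, before consent. But 8.5 is the clearest statement, and 8.7.2 agrees by linking enrolment to meeting the criteria at the end of the second screening visit. Tabulation by onset can be left to the SAP; the reporting window and the visit schedule are protocol matters, and analysis cannot recover events that nobody asked about.

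**Conclusion.** The point holds in two parts.

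- **Angiography:** on the meaning of enrolment in 8.5, reactions before enrolment are outside the stated AE period, and in screen failures the period never opens. This affects everyone who has the test at Screening 1.
- **Laser:** it is inside the period but followed by no solicited check for 8 to 21 days in the implant arm by Table 2 (up to about 57 to 60 days at the eight-week limit), or until about 6 to 8 weeks after randomisation in controls. Detection may be late and unequal, with some risk of confusion with device events.

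The number exposed to the laser gap is at most the 132 to be randomised; the protocol does not say how many will need the laser. The longer intervals assume that randomisation follows the laser by no more than 72 hours. The defect should be corrected, but misattribution is a risk and has not been shown.

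**What to change.** - **11.8:** start the AE period at signature of trial consent. For screen failures, keep it open until their last screening procedure.
- **Table 2 and 10.2.2:** add an AE question for both groups at the existing contact within 72 hours after the laser, asked before allocation is disclosed. This gives equal ascertainment, unaffected by knowledge of the arm.
- **Table 2 and 10.2.2:** add an AE question at the existing pre-operative visit. Only the implant arm has this visit, so it helps to date events before surgery but does not replace the question to both groups.
- **CRF:** record each AE's onset date relative to laser and surgery, so that events before surgery can be separated from events after implantation. The layout of the tables can go in the SAP.

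The cost is a few questions at contacts that already take place and slightly more AE records; no new visit or test is needed. One limit remains: the protocol does not state how the 72-hour contact is made, and a question alone will not detect an asymptomatic event.

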10.6.2 Statistical methods

The primary endpoint is the change from baseline of BCDVA at the 12-month time point in the study eye. The treatments will initially be compared using the independent t-test followed by a repeated measures analysis of covariance, adjusting for site, baseline BCDVA as a covariate and other covariates/factors where appropriate. Possible covariates/ factors will be discussed in the Statistical Analysis Plan (SAP) and may include size of scar, thickness of scar, and ocular dominance. Statistical diagnostic methods will be used to check for violations of the model assumptions and data transformations or non-parametric equivalents such as Mann-Whitney may be performed as appropriate. The primary data at 12 months are the BCDVA measurements by the independent assessor. The 12 month BCDVA data measured by the optometrist on the research team will be analysed as part of a sensitivity analysis.

The continuous secondary endpoints will be analysed in the same manner as the primary endpoint with an endpoint specific baseline covariate term included.

Analyses will be two-sided and tested at an a priori significance level of p=0.05. The primary time point has been defined as the 12-month time point. There is no adjustment for multiple testing at the different time points, as the primary outcome has been defined and prioritised.

For the mechanistic evaluation, descriptive statistics will be used to present the results. Also, the relationship between visual outcome and several factors (as discussed in Section 7.1) will be investigated using the independent t-test, 1-way analysis of variance, Pearson's correlation coefficient or non-parametric equivalents as appropriate depending on the scale of measurement of the factors.

Inter-rater reliability between the independent assessor and the optometrist on the research team will be tested for BCDVA at 12 months using the intra-class correlation coefficient.

Baseline characteristics, follow-up measurements and safety data will be described graphically and in tabular format using appropriate descriptive summary measures depending on the scale of measurement and distribution.

A detailed SAP will be written by the trial statistician prior to the final analysis.

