11 METHODS: MONITORING

b.4 Assessment of safety

The safety of device will be assessed at each visit by noting any surgical complications during or after surgery, including visual acuity, position and clarity of the device and corneal clarity. From previous studies it is known that loss of corneal endothelial cells following implantation of devices such as this is often biphasic i.e., there is an initial decrease following surgery then a continued loss for some months but at a lower rate. Stabilisation usually occurs at 12 months (13-16). The corneal endothelial count will therefore be repeated at month 12. It is not anticipated that the device itself will cause any systemic adverse events. A record will be kept of all Serious Adverse Events (SAEs). The CI will be responsible for informing the Sponsor, the Research Ethics Committee and all study sites about any SAEs. The DMEC will provide information on all SAEs on a routine basis.

b.4.1 Analysis of safety data

Adverse events (AEs, SAEs) will be listed and summarised by treatment. Incidents will be listed and summarised by treatment. Responses to the recent falls question will be tabulated. Endothelial cell densities will be listed.

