11.3 Definition of Adverse Events

As the current study is not investigating medical products, adverse event reporting will follow the Health Research Authority guidelines on safety reporting in non CTIMP studies. The PI or designee will make an assessment of seriousness as per the definitions below:

An **adverse event (AE)** is defined as any untoward medical occurrence in a participant in a research study, including occurrences which are not necessarily caused by or related to the study.

A serious adverse event (SAE) is defined as an untoward occurrence that:

- a) results in death;
- b) is life-threatening;
- c) requires hospitalisation or prolongation of existing hospitalisation;
- d) results in persistent or significant disability or incapacity;
- e) consists of a congenital anomaly or birth defect; or
- f) is otherwise considered medically significant by the investigator.

*Hospitalisation is defined as an inpatient admission regardless of length of stay, even if the hospitalisation is a precautionary measure for continued observation. Hospitalisations for a preexisting condition, including elective procedures that have not worsened, do not constitute an SAE.

b.4 Anticipated adverse events due to implantation of the OriLens

Below is a list of potential or anticipated Adverse Events based on prior IMT clinical trials or known to be occasionally associated with similar types of anterior segment surgery. This list should not be considered comprehensive, but rather identifies events which can be reasonably anticipated.

- Acute corneal decompensation
- Anterior segment neovascularizion
- Choroidal detachment
- Corneal oedema
- Cystoid macular oedema
- Endophthalmitis
- Fibrin in the anterior chamber
- Hyphema
- PC IOL dislocation
- OriLens device dislocation
- Inflammatory deposits on OriLens device
- Intraocular inflammation
- Iris transillumination defects
- Optic atrophy
- Posterior synechiae
- Removal of OriLens device
- Repositioning of OriLens device

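### Section 11.8 requires follow-up to resolution only for related and unexpected adverse events, which leaves out the 34 listed complications; separately, endothelial cell density has two conflicting analysis instructions

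*Protocol*

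**What the plan says.** **Follow-up of adverse events.** Section 11.8 sets the duty: "All AEs assessed by the PI or designee as being related and unexpected will be followed until they are resolved", or are clearly attributed to a stable or chronic condition or an intercurrent illness. The next sentence asks for the CRF to be updated with the date and time of resolution. The same section fixes the window: "The AE reporting period for the trial begins upon enrolment of a participant into the trial and ends at month 12".

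Section 11.7, on reporting SAEs to the ethics committee, defines the second condition: "Unexpected- that is, the type of event is not listed in the protocol as an expected occurrence". The list of anticipated events follows Section 11.3 and is introduced thus: "Below is a list of potential or anticipated Adverse Events based on prior IMT clinical trials", or as known to occur occasionally with similar anterior segment surgery. Section 11.6 adds: "All AEs will be assessed for seriousness, expectedness and relatedness by the PI or designee, recorded in the CRF".

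**Endothelial cell density.** The study summary places it among the key secondary outcomes, and Section 8.4.2 places it under Secondary Outcomes (safety of the device). Table 2 schedules specular microscopy for both groups at screening and month 12. On analysis, Section 10.6.2 says: "The continuous secondary endpoints will be analysed in the same manner as the primary endpoint", with an endpoint-specific baseline covariate. It also says that safety data will be described in graphs and tables. The analysis of safety data in Section 11 says: "Endothelial cell densities will be listed".

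**The concern.** A filter of related and unexpected suits expedited reporting to an ethics committee. As a rule for following events to their end it works backwards, because it leaves out the complications that the protocol itself anticipates from implantation. Endophthalmitis, retinal detachment, acute corneal decompensation, secondary glaucoma and device dislocation are all on the list. Device safety is a stated objective, and a safety report needs to say how such events ended as well as that they occurred. An analysis plan cannot recover outcomes that were never collected.

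Cell density is the measured form of the one device risk that Section 11.2 singles out, corneal endothelial damage. If the listing instruction were followed, the report would give individual counts without an estimate or interval for the loss.

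**Working it through.** **1. Which events fall under 11.8.**
- The rule is conjunctive: related and unexpected.
- Unexpected means a type not listed in the protocol (11.7).
- The anticipated-event list has 17 + 17 = 34 entries (the second 17 appear after the heading of Section 11.5).
- A listed event is therefore expected and fails the second condition, whatever its seriousness or relatedness. All 34 entries fall outside the duty.
- The sentence on date and time of resolution directly follows the rule and most naturally concerns the same events.

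**2. What still covers the listed events.** Every AE is assessed and recorded (11.6). Participants are asked about AEs at days 1 and 7 and months 1, 3, 6 and 12 (11.5), and ophthalmic examination is scheduled at those visits (10.2.2). An event that resolves between visits can be seen to have resolved. An event open at month 12 has no required outcome: the reporting period has ended, and Section 12.7 makes no specific post-trial provision.

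**3. The instructions for cell density, side by side.**

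| Place | Instruction |
|---|---|
| Summary; 8.4.2 | Secondary outcome, baseline and month 12 |
| 10.6.2, secondary endpoints | Analysed as the primary endpoint, with own baseline covariate |
| 10.6.2, safety data | Described in graphs and tables |
| Section 11, analysis of safety data | Listed |

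In the last of these, AEs and incidents are to be listed and also summarised by treatment, whereas densities are to be listed only.

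**4. The protocol's own figures.** Sample size (8.6): n = 2 × (1.960 + 1.282)² × 13.4² / 8.06² ≈ 58.1, so 59 per group; 59 / 0.90 = 65.6, so 66. Both reproduce.

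Appendix I, tolerable loss = (mean − 1500) / mean: 40.0%, 37.5%, 31.8% and 21.1%, against the stated 40, 38, 32 and 21. These also reproduce. A 20% loss from the minimum entry densities leaves 0.8 × 2600 = 2080, 0.8 × 2500 = 2000, 0.8 × 2300 = 1840 and 0.8 × 2000 = 1600 cells/mm². In the oldest band that is 100 above the 1500 limit.

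**5. Precision available for percentage loss.** The documents give no SD for cell loss; 10 to 20 percentage points is an assumption. With 59 per arm:
- Between arms, half-width of the 95% CI = 1.98 × SD × √(2/59): 3.6 (SD 10), 5.5 (SD 15), 7.3 (SD 20) points.
- Within one arm, half-width = 2.0 × SD / √59: 2.6 (SD 10), 5.2 (SD 20) points.

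The 20% in Appendix I is a predicted loss after telescopic implants, so the within-arm figure is the one to set beside it.

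**The case against.** **The events are not lost.** A reader might infer that listed complications go unrecorded or unwatched. The documents do not support that: recording, questioning and examination continue to month 12, and the monitoring committee's reports include AEs. What is missing is the explicit duty to follow to an end and record the outcome. This part of the objection stands and limits the harm.

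**The link between 11.7 and 11.8 is an inference.** The definition is written for SAE reports to the ethics committee, in the chief investigator's opinion, while 11.8 relies on the site investigator's assessment. That is so. It is still the natural reading: 11.8 repeats the same pair of conditions, 11.6 has every AE assessed for expectedness, and no other definition is given.

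**The list is mixed.** Some entries are procedures, such as corneal transplant or device removal, which do not resolve in the usual sense, and the protocol says that the list is not comprehensive. The count of 34 therefore measures the reach of the exclusion, not the number of events expected.

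**Cell density is a secondary endpoint.** A reader might infer from the listing sentence that cell loss will not be compared between arms. Section 10.6.2 read with 8.4.2 says otherwise, summary measures are promised for safety data, and a SAP that is not shown may settle the matter. Only the contradiction is established.

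**Judging loss against 20%.** A reader might set the between-arm half-width beside the 20% figure. That would be valid only if loss in controls were about zero, which the protocol does not state.

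**Conclusion.** The point holds in two limited parts.

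First, as worded, 11.8 places no duty to follow to resolution, or to record an outcome, on any of the 34 listed event types, including serious related ones. This rests on carrying the definition in 11.7 into 11.8. The practical loss is the outcome of listed events, mainly those still open at month 12.

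Second, the protocol gives cell density two incompatible instructions, a listing and a baseline-adjusted comparison between arms. They must be reconciled. The planned counts would support useful estimates: with 59 per arm and an assumed SD of 10 to 20 points, about ±2.6 to ±5.2 points within an arm and ±3.6 to ±7.3 points between arms. These figures move with the assumed SD.

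Both parts should be corrected. Neither bears on the primary analysis.

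**What to change.** **Section 11.8.** Reconcile the rule with the anticipated-event list, so that the duty of follow-up and outcome recording covers related AEs whether expected or not, and all SAEs, with status recorded at resolution or at last contact. The filter in 11.7 can stay for ethics committee reporting. This concerns what is recorded; it does not change how any complication is managed.

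**Analysis of safety data, Section 11.** Replace the listing sentence with one that agrees with 10.6.2:
- month-12 density compared between arms by ANCOVA with site and baseline density, with a 95% CI (there is one post-baseline count, so no repeated-measures term is needed);
- percentage loss summarised within each arm, for comparison with the 20% in Appendix I;
- the number below 1500 cells/mm² by arm.

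**Cost.** Two wording changes and a few more CRF entries for listed complications. Both cell counts are already scheduled in both arms.
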